All patients will have the right to withdraw their participation from the study at any time. Withdrawal will not affect their routine medical care. Patients may be withdrawn if it is thought to be in their best interests. The reason for withdrawal of any patient will be documented and any data gained up to the point of withdrawal may be used in analyses.

DATA ANALYSIS AND STATISTICAL METHODS

Paediatric Out-patient Population

Paediatric patients will be monitored simultaneously using the Aingeal and Capnostream devices for fifteen minutes over two phases (ten minutes at rest and five minutes during walking or playing). Before data collection commences, the time on the Surveillance Station will be verified against the time on the Capnostream device to ensure that respiratory data can be paired as closely as possible.

Heart Rate Comparison

Each of the ECG waveforms recorded by the Aingeal device will have heart rate calculated manually by a trained reviewer that has been blinded to the heart rate derived by the Aingeal device to minimise bias. Ten subjects will provide approximately 100 minutes (or 2 hours) of Aingeal data and approximately 100 heart rates. Both sets of heart rates will be compared using the approach of Bland Altman [1,2].

Respiratory Rate Comparison

The Aingeal device averages respiration rate over a 30 second window (or a period of 10 breaths, whichever is shorter). The respiration rate is updated each minute at the Surveillance Station. The Capnostream device stores data at resolution of 1 sample per second.

As a result there will be many more data points from the Capnostream device than from the Aingeal device over the same observation period. Ten subjects will provide approximately 100 minutes (or 2 hours) of Aingeal data and approximately 100 respiration rates. Both sets of respiratory rates will be compared using the approach of Bland Altman. Datasets will be stratified by age group as described in Table 1.

A total sample of 10 paediatric outpatients stratified by the age groups of 3 to 5 years old, 6 to 9 years old, 10 to 14 years old and 15 to 17 years old is estimated to provide an accuracy of 5% for respiratory rate, with estimated differences ranging from 0.7 to 1.25 breaths. The sample estimation is calculated based on a minimum of 8 repeated measures per child, having accounted for 20% attrition rate and 20% data loss due to signal loss, noise or time discrepancies.

Bland Altman Analysis

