The heart and respiration rate counts from each measurement method will be compared against each other in a pair-wise manner using the approach of Bland & Altman. For each parameter, this involves plotting the difference in the counts against the mean of the two absolute counts. The 95% and 99% limits of agreement, equivalent to 2 times standard deviation (sd) and 3 sd will be plotted. This process will be repeated for each portion of the test (at rest and during activity) and for each age group (3 to 5 years old, 6 to 9 years old, 10 to 14 years old and 15 to 17 years old) for heart rate and respiration rate. Adjustments for age and sex will be considered.

Feedback and Demographic Analysis

Summaries of patient, parent and HCP acceptability, demographics and medical history will be produced. In general, categorical data will be summarised using frequency counts and percentages, and continuous data will be summarised using means, standard deviations, minimums, medians and maximums.

RENEW'S AINGEAL PROCESS REQUIREMENTS

A. Application and Registration

No	Step by Step Application
1	Add patient to Central (Surveillance) Station.
2	Assign Aingeal Device to patient. (Pair the RENEW's Aingeal Device identifier code with Subject ID on the Surveillance Station and on the Patient Log)
3	Thoroughly clean the skin using alcohol wipes. Poor skin prep may result in poor signal quality.
4	Apply electrodes: Position the electrodes as shown in the figures below. RENEW's Aingeal Device should be placed on the left chest, just left of the centre of the sternum and below the collar bone. The right chest electrode should be placed just right of the centre of the sternum and below the collar bone. Place the electrode on the left side of the patient's body at the 7th rib and on the midline.
5	Connect device & start-up: Turn on RENEW's Aingeal device by pressing the "ON" Button. Check that the device beeps, that the Wi-Fi LED changes from orange to green, and that the Leads LED changes from blue to unlit.
6	Start Monitoring Patients on RENEW's Surveillance Station. Validate waveforms.
7	Check alarm limits.

[figure not shown]

Fig. A. Aingeal Device on adult

B. Data Collection and Validation

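### Separate limits of agreement for each age group would rest on about two or three children, with no term for repeated readings from one child, so on average they come out too narrow

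*Combined protocol and SAP*

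**What the plan says.** The Bland Altman Analysis section has the two sets of heart and respiration rates "compared against each other in a pair-wise manner using the approach of Bland & Altman". It adds: "The 95% and 99% limits of agreement, equivalent to 2 times standard deviation (sd) and 3 sd will be plotted". It then says: "This process will be repeated for each portion of the test (at rest and during activity) and for each age group", listing four groups (3 to 5, 6 to 9, 10 to 14 and 15 to 17 years). The only sentence on modelling is "Adjustments for age and sex will be considered". There is no term for the child, no repeated-measures version of the method, and no confidence interval for the limits.

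The sample size is under Respiratory Rate Comparison. A total of 10 children across the four age groups "is estimated to provide an accuracy of 5% for respiratory rate, with estimated differences ranging from 0.7 to 1.25 breaths". The basis is given as follows: "The sample estimation is calculated based on a minimum of 8 repeated measures per child". The estimate allows for 20% of children dropping out and for a further 20% of readings being lost. The number of children per age group is not stated. Table 1, which that section cites for the age groups, is not in the text available for this review, and its absence is not counted against the plan. Under Withdrawal and Discontinuation, "any data gained up to the point of withdrawal may be used in analyses", so a child who leaves early may still contribute some readings.

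**The concern.** Each child supplies roughly one reading per minute for up to 15 minutes. Differences between devices in the same child are likely to resemble one another, because electrode contact, body size and breathing pattern belong to the child. If the readings are pooled as separate pairs, the SD from two or three children mostly reflects variation within those children and misses much of the variation between children.

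A nominal 95% limit is meant to show where about 95% of device errors fall. If the age-group limits hold clearly fewer, agreement at that age looks better than it is. Validity in children aged 3 to 17 is the first aim of the study, and the plan does not label the age-group limits as descriptive. The stated 5% accuracy gives no protection here, because it is not derived for single age groups.

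**Working it through.** **Children per group.** 10/4 = 2.5. After 20% attrition, 10 × 0.8 = 8 and 8/4 = 2. Both assume a near-even split.

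**The plan's own figure.** Some pieces reproduce:
- 8/(1 − 0.20) = 10 children.
- 10 rest-phase readings × 0.8 = 8 readings per child.
- 0.7/0.05 = 14 and 1.25/0.05 = 25, so the range of differences may be 5% of breathing rates from 14 to 25 per minute. This is an inference; those rates are not in the documents.

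The 5% itself does not reproduce. Take 0.7 to 1.25 breaths as the half-width of a 95% interval, with 8 children × 8 readings. The effective number of readings is 64/(1 + 7r), where r is the within-child correlation: 64 at r = 0 and 8 at r = 1.
- If accuracy means the mean difference, SD = half-width × √n_eff / 1.96. This runs from 0.7 × √8/1.96 = 1.01 to 1.25 × √64/1.96 = 5.10 breaths.
- If it means a limit of agreement, divide by √(1 + 1.96²/2) = 1.709. This gives 0.59 to 2.99 breaths.

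The documents do not say which reading, SD or correlation was used, so the figure can be neither confirmed nor refuted.

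**How far the pooled SD falls short.** Let k children give m readings each, n = km, and σ be the true total SD of the differences. Then

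E[s²]/σ² = [1 − (1 + (m − 1)r)/n] × n/(n − 1).

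With m = 12 (15 × 0.8), k = 2 and r = 0.5: (1 + 11 × 0.5)/24 = 0.271, and (1 − 0.271) × 24/23 = 0.761. The square root is 0.872, so the SD is about 13% too small. With 3 children the factor is 0.918, and with 8 children 0.971. The centre of the limits is also poorly estimated with two children, which lowers coverage further.

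**Coverage.** Simulation with 40,000 runs per cell, normal differences, equal spread, no phase or age effect, and limits equal to the pooled mean ± 2s. The figure is the average share of all differences inside the limits (nominal 95.45%):

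| Basis (12 readings per child) | r = 0 | 0.3 | 0.5 | 0.8 |
|---|---|---|---|---|
| 2 children | 93.7% | 89.2% | 84.3% | 72.3% |
| 3 children | 94.3% | 91.4% | 88.3% | 80.7% |
| 8 children (whole sample) | 95.0% | 94.0% | 92.9% | 90.5% |

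Independent re-runs of the 2-child, 12-reading row agree within 0.2 percentage points. If age group and phase are crossed, which the sentence leaves open, an activity cell has about 5 × 0.8 = 4 readings per child. Two children then give 89.7/85.7/81.6/71.2% (20,000 runs).

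**What a child-level model recovers.** Four groups × 2 children × 12 readings, child random, age fixed, group mean ± 2 total SD: 94.9/92.5/90.4/86.2%, under equal spread.

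**The case against.** The strongest reply is that this is a small study which its own Conclusion describes as a test of feasibility, with no pass or fail criterion tied to age-group limits. Whole-sample limits, overall or by phase, are much less affected. That stands, and it confines the point to the age-group limits. It does not justify printing nominal 95% limits from two children without a caveat, in a document titled a validation study.

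Three stronger readings are tempting and are not supported:
- *The 5% accuracy has no basis, or ignores repeated measures.* The sample-size text gives a range of differences, at least 8 repeats per child and two 20% losses. What is missing is the SD, the within-child correlation, the confidence level and a definition of accuracy. The gap on repeated readings is in the analysis text.
- *The activity phase contradicts the 8-reading basis because it gives only 4 or 5 readings.* The 8 readings are per child, not per phase, and 15 × 0.8 = 12 exceeds 8. No 5% claim is made for activity, for an age group or for heart rate.
- *The age-group results are many times less precise, judged by intervals that take the child as the unit.* The plan computes no confidence intervals, so such multiples do not describe its output. The coverage figures do.

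Two or three children per group also remains an assumption. An uneven split could leave a group with fewer or more, and data kept from withdrawn children soften the attrition figure.

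**Conclusion.** The point holds as a gap in the analysis method. Followed as written, the plan gives age-group limits that are on average too narrow whenever differences correlate within a child. At a correlation of 0.5 they hold about 84% of differences with 2 children and 88% with 3, against about 93% for the whole sample of 8. At zero correlation the shortfall is 1 to 2 points (93.7% and 94.3% against a nominal 95.45%); at 0.8 with 2 children coverage is about 72%. The result rests on a near-even split, equal spread across groups, normal differences, 12 usable readings per child, and correlations that the documents do not give.

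The 5% accuracy cannot be reproduced from what is stated, which does not show that it is wrong. It should be read as applying to the total sample and to respiratory rate only. The point is worth correcting before analysis; it does not undermine the whole-sample comparison.

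**What to change.** For heart rate and respiratory rate, estimate bias and limits of agreement across all children with a repeated-measures Bland-Altman method: child as a random effect, age as a fixed effect, limits from the total (between- plus within-child) SD, and confidence intervals for bias and limits. Fit it separately for rest and activity, or allow phase-specific variances, so that the plan's phase-specific limits are kept. Phase as a fixed effect with one common SD would not do. If activity spread were 1.5 times rest (assumed, correlation 0.5), activity limits from one SD would hold about 85% of differences, against about 92% under the plan's separate whole-sample activity limits.

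Show age-group plots as descriptive, with the number of children and readings in each and without separate 2 sd and 3 sd limits. State the SD, within-child correlation, confidence level and meaning of accuracy behind the 5%, and do not extend it to age groups.

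The cost is text and analysis code; no extra children or readings are needed. The downsides are real:
- Age-specific limits are given up, because spread is assumed similar across ages. If one group's spread were 1.5 or 2 times that of the others (assumed, correlation 0.5), a range taken from a model with one common SD would hold 80.2% or 73.4% in that group, worse than the plan's roughly 84%.
- Between-child degrees of freedom are few: 8 − 4 = 4 with 8 children in four groups.
- Under-coverage for an age group is reduced, not removed: about 90% instead of 84% at correlation 0.5 under equal spread. That figure is for a single fit on 12 readings per child and was not computed for separate fits by phase.

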It was easy to set patients up on the Surveillance Monitoring Central Station.	1	2	3	4	5	9
RENEW's Aingeal Device was easy to apply onto the patient.	1	2	3	4	5	9
RENEW's Aingeal Device did not appear to increase patient's discomfort.	1	2	3	4	5	9
Loss of readings (vital signs) from RENEW's Aingeal Device was uncommon.	1	2	3	4	5	9
I was able to view and monitor my patient's vital signs on the Surveillance Monitoring Central Station easily.	1	2	3	4	5	9
I could have used RENEW's Aingeal Device without special training.	1	2	3	4	5	9
RENEW's Aingeal Device meets my clinical needs.	1	2	3	4	5	9
RENEW's Aingeal Device is safe for clinical use.	1	2	3	4	5	9
RENEW's Aingeal Device Surveillance Monitoring is easily integrated with the ward routine.						
RENEW's Aingeal Device Surveillance Monitoring enhances patient care delivered in the ward.	1	2	3	4	5	9

Additional comments	

	ID TAG
Questionnaire for Participants (Paediatric outpatient clinic)	
Date:	
Ward:	

Please answer all questions. Parents/Accompanying adults involved may provide assistance to children in responding to this survey. Take note that there is no right or wrong answer.

During the test of RENEW's Aingeal Device:	Strongly Disagree	Disagree	Neither Agree or Disagree	Agree	Strongly Agree
I was given adequate information on the RENEW's Aingeal Device to be used on my child/ward.	1	2	3	4	5
My child/ward is comfortable having RENEW's Aingeal Device on him/her all the time.	1	2	3	4	5
My child/ward does not have skin irritations from using RENEW's Aingeal Device .	1	2	3	4	5
My child/ward is able to continue with his/her daily activities with RENEW's Aingeal Device.	1	2	3	4	5
My child/ward is comfortable having his/her heart and respiratory rates monitored using RENEW's Aingeal Device.	1	2	3	4	5
If my child's vital signs need to be monitored for medical reasons, I would feel more secure with continuous monitoring of my child's heart and respiratory rates using RENEW's Aingeal Device than with periodic checks by hospital staff or nurses.	1	2	3	4	5

Additional comments

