- 3. The Aingeal device and Surveillance system are acceptable to Healthcare Professionals (HCPs), to paediatric patients, and to paediatric patients' parents or guardian.

STUDY DESIGN

Paediatric Out-patient Population

The Surveillance System will be installed in a paediatric outpatient clinic at KKH. A standalone Wi-Fi network will be set up to facilitate system use for the purposes of the study. Children attending the clinic aged between 3 and 17 years old will be invited to participate. Written consent from the child's parents or guardian will be obtained prior to participation.

Subsequent to obtaining consent, trained personnel will confirm the child's eligibility with their parent or guardian against the following inclusion and exclusion criteria:

Inclusion Criteria

- ✓ Male or female paediatric patients, aged between 3 and 17 years
- ✓ Patients attending outpatient care at KKH Women's and Children's Hospital, Singapore

Exclusion Criteria

- * Patients with active, implantable devices (such as a pacemaker or ICD)
- * Patients with any skin condition or injury affecting the electrode placement site
- **x** Patients that are pregnant
- * Those patients who, in the opinion of the outpatient clinic staff, are not suitable to participate.

Eligible and willing patients will be set up with an Aingeal electrode and device and Medtronic's Capnostream 35 portable respiratory cannula.

Recording of vital signs will begin at resting phase with the study subjects seated comfortably for 10 minutes. Younger children may be seated on the caregiver's or parents' lap. After the resting phase, the child will be asked to take a short walk around the clinic for 5 minutes. Younger children may be offered the playground instead.

Information on age, height, weight, sex and medical history will be collected from the patients' medical notes or reported by the patient's parent or guardian. At the completion of vital signs recording, feedback from the child and their parents or guardian will be obtained using self-reported questionnaires (Appendix 1).

Patient Identification

A patient enrolment log will be maintained at each investigational site. This enrolment log will link the identifiable patient to a study patient number which will be used on all study data.

Withdrawal and Discontinuation

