The RENEW's Aingeal is a wearable wireless device that measures single lead ECG and impedance pneumography waveforms to derive heart and respiration rates. Skin temperature is measured via a thermistor on the electrode patch. Every minute these parameters and a 25 second snapshot of waveform data are transmitted to the Surveillance Station over Wi-Fi.

The RENEW's Aingeal will be attached onto the Subjects for continuous monitoring during the Study.

- i. The Subjects will each be identified by a unique Subject ID assigned at time of recruitment and a Device ID using an agreed format.
- ii. Raw vital signs data ie. Readings, will be extracted from Surveillance System and provided to KKH research team for further study data mapping and analysis.

- iii. Sampling Rate will be derived using a data averaging method over a period of 60 seconds for the Capnostream data output. KKH requires all raw data points, in additional to per minute.
- iv. KKH will extract the averaging data points for further data processing and mapping against the Subject's demographics; e.g age, gender, height, weight etc.

For first week of the trial, Renew is required to extract the daily data files onsite and provide to KKH. This is to ensure that the setup is working well and correct data is collected and verified. There is no contact between the participants and the representative from the study sponsor. Also, the patient's details will not be keyed into the system as we will only put participant's subject ID number, which will not allow sponsor to identify the patients. Removal and De-Registration

No	Step by Step Application
1	Turn off the RENEW's Aingeal by pressing and holding the "OFF" Button on the RENEW's Aingeal until the green LED is unlit.
2	Remove the RENEW's Aingeal gently from the Subject
3	Slowly and carefully remove the electrodes from the Subject
4	The subject can be discharged from the Surveillance Station after data collection has completed and all required data is collected.
5	Dispose the electrodes appropriately into designated bins.

C. Training Plan

The training program is designed to provide the relevant study team members with sufficient knowledge and skills to configure and use the RENEW Surveillance System. The program will comprise of interactive instructor led clinical demonstration.

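### Two of the six participant questionnaire items ask beyond the roughly 15-minute clinic test, and the skin item can show only an immediate reaction

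*Combined protocol and SAP*

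**What the plan says.** Objective 3 (Aims & Objectives) is to determine whether "The Aingeal device and Surveillance system are acceptable to Healthcare Professionals (HCPs), to paediatric patients" and to their parents or guardian.

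The exposure is set out in Study Design: "Recording of vital signs will begin at resting phase with the study subjects seated comfortably for 10 minutes", after which "the child will be asked to take a short walk around the clinic for 5 minutes"; younger children may use the playground instead. Data Analysis and Statistical Methods gives the same total, with monitoring "for fifteen minutes over two phases (ten minutes at rest and five minutes during walking or playing".

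On timing, Study Design states: "At the completion of vital signs recording, feedback from the child and their parents or guardian will be obtained using self-reported questionnaires". No later contact is described. Electrode removal appears separately, as step 3 of the Removal and De-Registration table: "Slowly and carefully remove the electrodes from the Subject". Neither place says whether the form comes before or after that step.

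The Questionnaire for Participants in Appendix 1 has six items rated 1 to 5 under a stem that refers to the test of the device. One reads "My child/ward is able to continue with his/her daily activities with" the device. Another asks whether the child is comfortable wearing it 'all the time', and a third whether the child is free of skin irritation from it. Respondents are asked to answer every question. The staff form in the same appendix has a Not Applicable column; the participant form does not.

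Feedback and Demographic Analysis plans descriptive summaries of acceptability, generally counts and percentages for categorical data. It sets no acceptability threshold.

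**The concern.** A questionnaire can report experience only of what the respondent has seen. Here the parent sees one short supervised test but is asked to rate wear without a time limit and ordinary daily life. With no way to mark an item as not experienced, a parent must leave the instruction unmet, use the neutral category, or guess. In the tabulated results a guess looks the same as an observation.

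The skin item has a timing problem as well. If the form is filled in while the electrodes are on, the skin beneath them is hidden. If it is filled in straight after removal, a later reaction cannot yet have appeared. In either case a parent who sees nothing is likely to agree that there is no irritation.

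At stake is the meaning of the parent results for a stated objective. The Conclusion of the protocol looks ahead to a role for the system in clinical monitoring and early warning for children, so a reader could easily carry these answers over to longer use than was tested.

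**Working it through.** **Exposure.** From Study Design, 10 min seated + 5 min active = 15 min. This reproduces the fifteen minutes given in Data Analysis and Statistical Methods. Time for set-up and removal is not stated, so actual wear is somewhat longer. The active phase is 5/15 = 33% of monitored time.

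**Items against exposure.** The six rated items, paraphrased:

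| Item | What the visit can inform |
|---|---|
| Enough information was given | Experienced |
| Comfortable with the device on 'all the time' | Only if read as throughout the test |
| No skin irritation | Immediate reaction only, and only once the site is uncovered |
| Can continue daily activities | Only a 5-minute walk or play |
| Comfortable having heart and respiratory rates monitored with the device | Experienced |
| Would feel more secure with continuous monitoring than periodic checks, if monitoring were needed | Openly hypothetical; asks for a preference |

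**Counts.**
- Items that ask beyond the visit: 2 of 6 = 33%.
- Adding the skin item, which is answerable in part: 3 of 6 = 50%.
- Across both forms (6 participant + 10 staff = 16 rated items): 3/16 = 19%.

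**Effect on a percentage.** The planned sample is 10 children. Assuming one participant form per child and all returned, one answer moves an item's percentage by 1/10 = 10 points. A few parents reading an item differently would visibly change the reported figure.

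**Opt-out.** The staff form offers Not Applicable where a question does not fit the respondent's duties. The participant form offers five points only, with an instruction to answer everything. The midpoint records a neutral opinion, which is not the same as not having observed the matter.

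**Order of steps.** Completion of recording is compatible with the form coming either before or after electrode removal. The order is unspecified; it is not shown to be wrong.

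**Direction of error.** For the skin item, a hidden site or a delayed reaction pushes answers towards agreement, which favours the device. For the other two items the documents give no basis for a direction.

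**The case against.** The strongest reply is that the stem ties every item to the test, so 'all the time' can be read as throughout the test, and the walk or playground gives real, if brief, experience of moving with the device. This stands in part: the two items are not empty. But they are worded as general statements in the present tense under a stem about the test. Some parents may answer for the 15 minutes and others for ordinary life, and the data will not show which.

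A second reply is that parents are not forced to take sides, because a neutral category exists and there is space for comments. That softens the problem without removing it, since a neutral answer cannot be separated from one that means not observed.

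Three stronger readings are tempting, and the documents do not support them.
- A reader might infer that objective 3 as a whole rests on things nobody experienced. It does not: staff have their own form of 10 rated items, and at least two participant items concern things that happened in the visit.
- A reader might infer that the skin item is worthless. Immediate irritation can be seen once the electrode is off; what is missed is a delayed reaction.
- A reader might set 15 minutes against a full day of wear, or expect the results to be reported as acceptance of continuous wear. No wear period is stated, the planned analysis is descriptive, and the Conclusion frames the study as a test of feasibility.

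**Conclusion.** The point holds in a limited form. Two of six participant items (33%) ask beyond a roughly 15-minute exposure. A third, on skin, can be answered only for an immediate reaction, and only if the form follows electrode removal. With every item to be answered and no Not Applicable option, the parent part of objective 3 would rest partly on expectation.

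This assumes that the form is used as printed, that it is completed at the visit, and that some parents will read the two items as going beyond the test. The last of these is a judgement about wording that the documents cannot settle.

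The heart rate and respiratory rate agreement analyses, the staff form and the remaining participant items are untouched. The matter concerns a descriptive aim, but no analysis can separate the two kinds of answer once the forms are in, so it is worth correcting before use.

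**What to change.** 1. Reword the two items to the visit, for example: *My child was comfortable wearing the device during today's test* and *My child was able to walk or play normally while wearing the device*. Add a Not Applicable option to the participant form and report its count for each item.
2. State that the form is completed after electrode removal (Removal and De-Registration, step 3), and word the skin item as irritation visible at removal.
3. Limit the parent acceptability conclusion to short clinic use, with no claim about prolonged wear or delayed skin reactions.

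The cost is a short amendment to the form and a stated order for two end-of-visit steps, with no extra visits or participants. The downside is a narrower acceptability claim.
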